9.5.4 Reporting Responsibilities

All SAEs (excepting those specified in this protocol as not requiring reporting) will be reported immediately (and certainly no later than 24hrs) by the Investigator to the GSTT R&D Office and CI for review in accordance with the current Pharmacovigilance Policy. The Chief Investigator will report to the relevant ethics committee. Reporting timelines are as follows:

The Chief Investigator (on behalf of the co-sponsors), will submit a Development Safety Update Report (DSUR) to the MHRA and REC annually.

9.6. Trial Management Group

Study management meetings will be held approximately every two months (with video conferencing where required). All researchers and clinicians affiliated with the project will be invited to participate in these meetings which will allow discussion of all aspects of the programme and the timely addressing of issues as they arise.

9.7. Trial Steering Committee (TSC)

The role of the Trial Steering Committee (TSC) is to provide the overall supervision of the study. The TSC will monitor the progress of the study and conduct and advise on its scientific credibility. The TSC will consider and act, as appropriate, upon the recommendations of the DMC and ultimately carries the responsibility for deciding whether the trial needs to be stopped on the grounds of safety or efficacy. The TSC will consist of an independent chair and at least two other independent members (not involved in study recruitment and not employed by any organisation directly involved in study conduct. A representative from our dedicated preterm birth studies Patient Public Involvement group will be invited to participate. The first meeting will take place 6 months after trial start date; frequency will be decided at the first meeting (at least annually).

9.8. Data Monitoring Committee (DMC)

A DMC independent of the applicants and TSC will review the progress of the trial at least annually and provide advice on the conduct of the trial to the TSC. The committee will periodically review study progress and outcomes. The timings and content of the DMC reviews will be detailed in a DMC charter which will be agreed at its first meeting. The DMC will meet 3 months following study commencement/recruitment of the first participant ; frequency of meeting will be decided at the first meeting.

9.9. Study Coordinating Centre

The trial coordinating centre will be the Department of Women and Children's Health, Kings College London, where the study coordinator will be based. The Division of Women's Health will be responsible for statistical analysis, servicing both the DMC and the Trial Steering Committee (TSC) and, in collaboration with the Principal Investigators, study coordinator and Local Research Midwives/Nurses, for the day to day running of the study including recruitment of sites and training of staff.

9.10. Trial stopping rules

Study Protocol: **Cerclage After Full-dilatation caesarean-section**
IRAS ID:261294
REC: REC 19/LO/1270
Version 2.0
Date: 10.09.19

The CRAFT-RCT trial may be prematurely discontinued by the Sponsor, Chief Investigator or Regulatory Authority on the basis of new safety information or for other reasons given by the DMEC/TSC regulatory authority or ethics committee concerned. If the trial is prematurely discontinued, active participants will be informed and no further participant data will be collected. The Competent Authority and Research Ethics Committee will be informed within 15 days of the early termination of the trial.

10. Investigator responsibilities

The Investigator is responsible for the overall conduct of the study at the site and compliance with the protocol and any protocol amendments. In accordance with the principles of GCP, the following areas listed in this section are also the responsibility of the Investigator. Responsibilities may be delegated to an appropriate member of study site staff. Delegated tasks must be documented on a Delegation Log and signed by all those named on the list.

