Over 25% of all deliveries in the UK are by CS and up to 20% of in labour caesarean sections occur at full dilatation, which could affect up to 20,000 women in the UK per annum (8). These women have a six-fold increased incidence of subsequent preterm birth compared with women who undergo CS in the first stage of labour (adjusted odds ratio 5.8; 95% confidence interval 1.08-30.8)(3); 13.5% in comparison with 2%. This equates to around 2500 women per year in the UK. In women who lose a pregnancy, more than half will also go on to experience recurrent pregnancy losses in spite of intervention, compared to 14% of women with a history of preterm birth without previous FDCS (relative risk 3.06 95% confidence interval 1.22-7.71)(9). The relative risk of PTB in women with a previous emergency CS earlier in labour is unknown, however it is thought to be a continuum of risk, i.e. the later in labour the CS is carried out, the higher the risk of PTB in future pregnancies.

A screening programme to assess for cervical shortening in women with a previous FDSC is due to be implemented as part of new NHS commissioning guidance(1) and the revised *Saving Babies Lives Care Bundle*(2). It is unknown whether transvaginal cervical length screening for a short cervix predicts outcome in this group and there is currently limited evidence to inform optimal management of these women. It is also unknown whether first-line interventions for short cervix $\leq 25\text{mm}$ (vaginally-placed cerclages inserted in the distal cervix during pregnancy), used in other high-risk groups of women, is effective in this cohort. Preliminary data indicates that these interventions may be less efficacious, likely due to the injury having occurred in the proximal cervix, above the cerclage. A small retrospective analysis indicated that of 19 women who had experienced a LM/PTB subsequent to a FDSC and who then had a cerclage in the 3rd pregnancy, 10 (53%) still delivered <30 weeks gestation in comparison with 3% of a high-risk control group, who also had a cervical cerclage in situ after a LM/PTB (n=154).

This study has been developed in collaboration with the Preterm Birth Studies PPI Group at St Thomas' Hospital. They have confirmed that this issue is of vital importance to them and they will be consulted on all study literature and future directions associated with this project.

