4.1. CRAFT-OBS

Primary endpoint:

- i) Delivery < 37 completed weeks gestation (powered).

Secondary endpoints

- i) Adverse perinatal outcome, defined as a composite outcome of death (ante-partum/intra-partum stillbirths plus neonatal deaths prior to discharge from neonatal services)
- ii) Delivery <34 weeks gestation.
- iii) Gestation at delivery.
- iv) Late miscarriage (14⁺⁰-23⁺⁶ weeks).
- v) Healthcare use, e.g. appointments, hospital admission, cervical length, cervicovaginal fetal fibronectin levels, interventions.
- vi) Predictive modelling to evaluate the ability of CL and fFN to determine risk of preterm birth <34 and <37 weeks
- vii) Other maternal and fetal morbidities, as per COPOP core outcome set for preterm birth intervention studies(15).

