4.3. CRAFT-IMG

Primary endpoint:

- i. Alterations in imaging parameters between women with a full dilatation C-section in a previous pregnancy and either a cervix $\leq 25\text{mm}$ or a cervix $>25\text{mm}$ in this pregnancy which culminates in a preterm (<37 week) delivery.

5. Sample size and power calculation

All power calculations were performed by the trial statistician [name].

CRAFT-OBS: With estimated prevalence of 15% preterm birth rate prior to 37 weeks, and 16.2% of all deliveries being by emergency caesarean section; we will require data on 2200 women to estimate the event rate to 10% relative accuracy (e.g. 13.5% to 15.6%).

An average district general hospital has 4,000 deliveries per year, of which 648 (16.2%) might be by Emergency Caesarean. We aim to recruit 324 of these (50%) at a minimum of 7 study sites. At St Thomas' Hospital rather fewer deliveries (11%) are caesareans in labour; so we will aim for at least 20 sites, taking the assumptions above into account.

If we acquire data of cervical length and/or quantitative fetal fibronectin in this cohort, we will be able to validate these prediction tools. If we treat a short cervix of $\leq 25\text{mm}$, and a raised qfFN of $\geq 50\text{ng/ml}$ as positive tests, we anticipate a 75% sensitivity and 83% specificity from the literature for both tests (16).

Assuming 10% event rate, 1000 women (100 cases and 900 controls) would allow use to estimate the sensitivities of qfFN and CL to within 10% and the specificities to within 3% of the true value. The PPV would be estimated within 7% and NPV within 1.5% of their true values.

CRAFT-RCT: Pilot data indicates that at least 10% of all births and 70% of preterm births associated with FDCS occur before 34 weeks. In order to detect a reduction in this rate from 10% to 5% 474 women are required in each group to give 80% power. We will aim to recruit 500 in each arm in order to allow for 5% loss to follow-up.

CRAFT-IMG: We consider that the participation of 60 women in this sub-study will provide useful information for planning future research; this is achievable by recruiting at 2 sites (UCLH and St Thomas' Hospital): 30 women with cervix $>25\text{mm}$ and 30 women with cervix $\leq 25\text{mm}$ (15 women with cerclage, 15 women without).

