Serial MRI scans will be performed on a 3-Tesla MRI scanner at St Thomas' Hospital. Conventional imaging will include high resolution T1 and T2 weighted images as well as diffusion datasets. The first advanced protocol transvaginal ultrasound and MRI will occur at any time from 20 weeks gestation. Where delivery has not occurred, further imaging will be offered (up to a maximum of 3 MRI and 3 of these transvaginal ultrasound scans).

Outcome data: All participants' data will be collated up until postnatal discharge. Neonates will be followed up until discharge or 28 days (whichever is sooner). Prompts on the database will alert the research midwife/assistant when each trial participant reaches her delivery date. Birth registers and in-patient records will be used to track hospital admissions and pregnancy outcomes. Outcome data (medical and economic) will be collected by review of NHS Maternity and medical records. If information is unavailable, e.g. if the delivery occurred elsewhere, the patient, patient's GP or other hospital will be contacted. Gestational age will be calculated using Study Protocol: **Cerclage After Full-dilatation caesarean-section**

IRAS ID:261294

REC: REC 19/LO/1270

Version 2.0

Date: 10.09.19

ultrasound estimated date of delivery predicted at the 12-15 week ultrasound scan. The primary and secondary outcome data will be collected from hospital records after discharge from neonatal care.

Source data and documents will be accessible by the research team only and any paper records will be stored in a locked cabinet in the Principal Investigators' offices. Electronic versions of these source documents are stored on Trust computers only and behind the NHS firewall. The study may be subject to inspection and audit by King's College London and Guy's and St Thomas' NHS Foundation Trust under their remit as sponsor and co-sponsor respectively, and other regulatory bodies to ensure adherence to GCP and the NHS Research Governance Framework for Health and Social Care.

The identifiable information obtained as part of this study will be managed in accordance with the General Data Protection Act (2018). The computerised information is protected by a software and hardware barrier, and the records are handled in the same way as hospital records. Data will be stored for 25 years in Trust firewalls/KCL Firewalls in accordance with legal requirements for the storage of maternity records.

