9.5.2 Procedures for Recording and Reporting Adverse Events

Serious adverse Event (SAE), Serious Adverse Reaction (SAR)

The Medicines for Human Use (Clinical Trials) Regulations 2004 and Amended Regulations 2006 gives the following definitions:

Adverse Event (AE): Any untoward medical occurrence in a subject to whom a medicinal product has been administered including occurrences which are not necessarily caused by or related to that product.

Adverse Reaction (AR): Any untoward and unintended response in a subject to an investigational medicinal product which is related to any dose administered to that subject.

Unexpected Adverse Reaction (UAR): An adverse reaction the nature and severity of which is not consistent with the information about the medicinal product in question set out in the Investigator's Brochure (IB) relating to the trial in question (for any other investigational product)

Serious adverse Event (SAE) or Serious Adverse Reaction (SAR) is:

Any adverse event, adverse reaction or unexpected adverse reaction, respectively, that

- Results in death
- Is life-threatening
- Required hospitalisation or prolongation of existing hospitalisation, excluding admission for birth or unrelated pregnancy condition
- Results in persistent or significant disability or incapacity
- Is otherwise considered medically significant by the principal investigator.

All AEs and SAEs must be recorded from the time a participant is randomized to treatment until 30 days after stopping taking study drug and until pregnancy outcome (28 days after delivery). The Investigator should ask about the occurrence of AEs/SAEs at every visit during the study. Open-ended and non-leading verbal questioning of the participant should be used to enquire about AE/SAE occurrence. Participants should also be asked if they have been admitted to hospital, had any accidents, used any new medicines or changed concomitant medication regimens. If there is any doubt as to whether a clinical observation is an AE/SAE, the event should be recorded. Hospitalisations for treatment planned prior to randomisation and hospitalisation for elective treatment of a pre-existing condition will not be considered as an SAE. Complications occurring during such hospitalisation will be AE/SAEs.

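### Section 9.10 ends data collection if CRAFT-RCT stops early, with no exception for women already randomised and still awaiting their primary outcome

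*Combined protocol and SAP*

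**What the plan says.** Section 9.10 allows CRAFT-RCT to be stopped early and names new safety information as the first ground. It then says: "If the trial is prematurely discontinued, active participants will be informed and no further participant data will be collected". Neither that section nor any other exempts women who have already been randomised.

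Other sections that bear on the point:

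- **Sections 6.2 and 4.2.** RCT entry is at 14+0 to 23+6 weeks. The primary endpoint is delivery before 34 weeks. Secondary endpoints include gestation at delivery and a composite of perinatal death and neonatal morbidity.
- **Section 8.** The primary analysis is by intention to treat. No method is given for randomised women whose outcome is unknown.
- **Section 7.3.** Women are followed to postnatal discharge, and neonates to discharge or 28 days, whichever is sooner. "The primary and secondary outcome data will be collected from hospital records after discharge from neonatal care".
- **Section 9.5.2.** Adverse events are recorded from randomisation until 28 days after delivery.
- **Sections 7.1 and 4.1.** RCT women are drawn from CRAFT-OBS, whose secondary endpoints include "Delivery <34 weeks gestation".
- **Section 9.8.** An independent committee "will review the progress of the trial at least annually"; its charter is to fix the timing and content of reviews.

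**The concern.** A woman's primary outcome is settled only when she delivers or reaches 34 weeks, which is 10 to 20 weeks after entry. At any stop during recruitment, a block of recently randomised women is therefore still open. If collection ceases that day, they cannot be analysed as randomised, because their outcome is never obtained. The analyst must then drop them or assign them a status, and the plan does not say which.

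The two crude choices err in opposite directions. Events become known before non-events, so using known outcomes only inflates both event rates. Counting every undelivered woman as a non-event deflates them.

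The loss extends beyond the primary endpoint. An undelivered woman past 34 weeks has a primary outcome but no gestation at delivery, no perinatal composite and no further safety record. If the stop was made on safety grounds, those are the data most needed.

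**Working it through.** Section 9.10 contains no figure to reproduce. The rates used here, 10% and 5%, are those of section 5. The 474 per arm stated there is reproduced by a two-sided 5% test with continuity correction and 80% power (the significance level is an assumption, as the plan does not state it).

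**Inputs from the protocol.** Entry at 14+0 to 23+6 weeks (6.2); endpoint at 34 weeks (4.2); 1000 women over 24 months (3.4) or 27 months (3.2), which is 9.58 or 8.52 women per week.

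**Assumptions, not in the protocol.** Steady accrual; entry uniform over 14 to 24 weeks; a stop at 12 months (52.2 weeks); deliveries up to the stop known promptly. Events before 34 weeks fall early, uniformly or late in the interval from entry to 34 weeks, at a mean of 1/3, 1/2 or 3/4 of it.

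**Step 1: share with unknown 34-week status.** The mean time from entry to 34 weeks is 34 − 19 = 15 weeks. Let m be the mean time from entry to an event: 5, 7.5 or 11.25 weeks. For an arm with event rate p,

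unknown share = [(1 − p) × 15 + p × m] / 52.2.

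For the control arm with uniform timing: (0.90 × 15 + 0.10 × 7.5) / 52.2 = 14.25 / 52.2 = 27.3%. For cerclage: (0.95 × 15 + 0.05 × 7.5) / 52.2 = 14.625 / 52.2 = 28.0%. The weekly accrual rate cancels, so the choice between 24 and 27 months does not alter the percentages.

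**Step 2: estimates under the two crude rules.** The observed event share is p × (1 − m / 52.2). That is the estimate if undelivered women count as non-events. Dividing it by (1 − unknown share) gives the known-outcomes-only estimate. The true values are 10% v 5%, difference 5 points.

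| Event timing | Unknown, both arms | Known only | Difference | Undelivered as non-events | Difference |
|---|---|---|---|---|---|
| Early | 27.3% | 12.4% v 6.3% | 6.1 | 9.0% v 4.5% | 4.5 |
| Uniform | 27.7% | 11.8% v 5.9% | 5.8 | 8.6% v 4.3% | 4.3 |
| Late | 28.2% | 10.9% v 5.5% | 5.4 | 7.8% v 3.9% | 3.9 |

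The bias in the difference is +0.4 to +1.1 points under the first rule and −0.5 to −1.1 under the second. If event timing is the same in both arms, the known-only odds ratio stays at its true value of 0.474, because the same fraction of events, and of non-events, is seen in each arm.

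**Step 3: counts.** Twelve months of accrual gives 444 women (27-month plan) to 500 (24-month plan). The unknown number is 0.273 × 444 = 121 to 0.282 × 500 = 141.

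**Step 4: sensitivity to entry and accrual.** If all women entered at 24 weeks, the mean wait is 10 weeks and the unknown share 18–19%. If all entered at 14 weeks, the wait is 20 weeks and the share 36–38%. If recruitment climbs linearly from zero, about 47% are unknown at 12 months.

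**Step 5: precision.** With 500 randomised and complete data, the 95% half-width of the difference is 1.96 × √[(0.10 × 0.90 + 0.05 × 0.95) / 250] = 4.6 points. With uniform timing and known outcomes only, about 181 women per arm remain, and it is 1.96 × √[(0.118 × 0.882 + 0.059 × 0.941) / 181] = 5.8 points.

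**The case against.** The strongest reply is that section 9.10 concerns CRAFT-RCT only. Every RCT woman is also a CRAFT-OBS participant, CRAFT-OBS records delivery before 34 weeks and gestation at delivery, and NHS numbers are collected for tracking (section 7.2). A reader might infer that 9.10 shuts off all data on these women. The documents do not support that: CRAFT-OBS is not stopped by 9.10 and may well supply their delivery outcomes. But they do not say that it will. Section 7.3 states that a woman who declines the RCT stays in the observational part with outcomes collected after birth; nothing equivalent is written for a randomised woman after a stop.

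It can also be said that section 9.5.2 sets its own safety window. It does, but it does not mention early stopping, so it and 9.10 give different instructions.

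The statistical reply is also fair. Because the cut-off is administrative, weighting observed events by the probability of remaining uncensored recovers 10.0% v 5.0% under the same assumptions, with a half-width of 4.9–5.3 points against 4.6 for complete data. That confirms that bias is not the main issue. The plan names no such method, however, and weighting cannot restore secondary or safety data that were never collected.

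Three further inferences go too far:

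- The late collection described in section 7.3 might suggest that women already delivered at the stop are lost as well. That depends on how strictly 9.10 is applied to records not yet extracted, which the text does not settle.
- The 27–28% might be set against the loss allowance in section 5. That allowance is for the completed trial and is no benchmark for a truncated one.
- The 12-month stop might be read as a planned look. It is only an illustration, since review timings are left to the charter.

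**Conclusion.** The concern holds as a conflict between a written rule and the rest of the plan. Followed literally, section 9.10 denies an RCT primary outcome to randomised women who are undelivered and under 34 weeks at the stop. It also denies secondary and safety outcomes to all undelivered women.

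At a 12-month stop this is 27–28% of those randomised, or 18–38% across the extremes of entry gestation. These figures rest on steady accrual and prompt knowledge of deliveries; a slow start to recruitment would raise them. The bias in the risk difference from crude handling, about 0.4–1.1 points under uniform entry, is small beside a half-width of at least 4.6 points. The documents therefore do not support a claim that an early-stopped result would be seriously biased. The real cost is randomised women, precision, secondary outcomes and safety follow-up. The planned analysis of a completed trial is unaffected. The rule should be corrected before any decision to stop is in view.

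**What to change.** Keep the commitment to inform participants, and replace the clause that ends data collection with:

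> Outcome and safety data for all women already randomised will continue to be collected from NHS records to delivery and the planned neonatal end-point, unless a woman withdraws consent to data collection or the regulator or ethics committee directs otherwise, and all will be analysed by intention to treat.

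Reconcile section 9.10 with sections 7.3 and 9.5.2, and state that CRAFT-OBS collection continues for these women.

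The cost is record review after a stop: from entry at 14+0 to delivery at 40–42 weeks is 26–28 weeks, plus up to 28 days, so at most about 7 months. The records route (7.3) and NHS-number tracking (7.2) are already planned. A protocol amendment is also needed; if it is substantial, section 10.6 requires approval from the ethics committee, the regulator and local R&D offices, with at least 41 hospitals planned. The consent pages are not in the documents reviewed, so whether existing consent covers collection after a stop should be checked.

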10.1. Data Handling

All electronic data will be stored behind a secure firewall. Clinical information will be handled as appropriate for Trust patients to ensure maximum and efficient communication of results and clinical details to the appropriate clinical teams. Any patient identifiable data transferred from behind the firewall will be anonymised prior to transfer. This will only be used with authorised collaborators with explicit knowledge of how the data is being used.

The Principal Investigator is responsible for the quality of the data recorded in the electronic clinical research files. The Chief Investigator will act as custodian for the trial data. Patient data will be anonymised. All anonymised data will be stored on a password protected computer. All trial data will be stored in line with the Data Protection Act as defined in the Kings Health Partners Clinical Trials Office Archiving SOP.

